5.6.3 Concomitant Treatments

5.6.3.1 Prohibited and Restricted Medications (Modules 1, 2, and 3)

Medications or vaccinations specifically prohibited in the exclusion criteria are not allowed during the ongoing trial. If there is a clinical indication for any medication or vaccination specifically prohibited during the trial, discontinuation from study intervention or vaccination may be required. The investigator is to discuss prohibited medication/vaccination with the Sponsor's Clinical Director. The final decision on any supportive therapy or vaccination rests with the investigator and/or the participant's primary physician. However, the decision to continue the participant on study treatment requires the mutual agreement of the investigator, the Sponsor, and the participant.

The following concomitant medication is prohibited:

1. The use of any natural/herbal products or other 'folk remedies'.
2. No other chemotherapy, or other anticancer therapy, including radiation therapy (except local treatment to a symptomatic solitary lesion), immunotherapy, and hormonal therapy (contraception and hormone replacement therapy is acceptable), or other investigational product is permitted other than the study treatments.
3. The use of some CYP3A4 inhibitors and inducers should be restricted prior to first dose of study treatment and throughout the study treatment, as RXC004 is observed to be exclusively metabolised by CYP3A4. For a list of prohibited CYP3A4 inhibitors and inducers and details of restrictions prior to the first dose of study treatment, please refer to Appendix E.

4. Drugs that are immunosuppressive or may cause secondary osteoporosis should not be administered (e.g. corticosteroids, pioglitazone or rosiglitazone). The following exceptions are allowed:
 - Use of immunosuppressive medication for the management of colitis events (per Appendix K), or pembrolizumab-related AEs (please refer to Appendix L).
 - Steroids required for the management of RXC004- or pembrolizumab-related AEs should be tapered to prednisolone \leq 10 mg/day equivalent, before re-starting study treatment.
 - Systemic glucocorticoids when used for the following purposes:
 - To modulate symptoms of an AE that is suspected to have an immunologic aetiology
 - For the prevention of emesis
 - To premedicate for IV contrast allergies
 - To treat chronic obstructive pulmonary disease (COPD) exacerbations (only short-term oral or IV use in doses $>$ 10 mg/day prednisone equivalent)
 - For chronic systemic replacement not to exceed 10 mg/day prednisone equivalent
 - Other glucocorticoids when used for the following purposes:
 - For topical use or ocular use
 - Intraarticular joint use
 - For inhalation in the management of asthma or COPD.
5. Live or live-attenuated virus and bacterial vaccines should not be administered, e.g. yellow fever, measles, influenza nasal spray, COVID-19, rubella, mumps, typhoid, mycobacterium *tuberculosis* (BCG), *Yersinia pestis* (EV) within 30 days of starting study treatment, whilst the patient is receiving study medication and for 30 days following discontinuation of study treatment. Killed vaccines are allowed. Patients who require COVID-19 vaccination whilst on study should receive a non-live vaccine (e.g. one based on mRNA or fully inactivated/genetically modified viruses incapable of replication). Investigational vaccines (i.e., those not licensed or approved for Emergency Use) are not allowed.

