5.1 Core Inclusion Criteria

Participants are eligible to be included in the study only if all of the following criteria apply:

1. Participant must be ≥ 18 years of age at the time of signing the informed consent.
2. Ability to give written informed consent and capable of understanding the protocol requirements listed in the informed consent form (ICF) and in this protocol. Written informed consent must be obtained prior to performing any protocol-related procedures, including screening evaluations. Participants must be willing and able to comply with the study protocol procedures and restrictions.
3. At least one lesion that is measurable by RECIST 1.1 at baseline (within 6 weeks prior to start of study treatment). The measurable lesion must not be chosen for the mandatory paired biopsies.
4. Mandatory paired biopsies; Patients must have at least one lesion suitable for biopsy at screening (which must not be a target lesion for RECIST 1.1) and be willing to provide mandatory tumour biopsy samples as follows:
 - (i) Baseline* (mandatory and must be performed before study treatment commences, except in exceptional circumstances where biopsy is not technically feasible. All patients without a baseline sample must be approved by Sponsor before starting study treatment as a minimum number of 5 paired biopsies per module are required to achieve the study objectives).
 - (ii) On treatment at C1D15 (+ 7 days). The C1D15 tumour biopsy is also mandatory and should be performed unless the investigator judges that this biopsy is contraindicated (high risk biopsy as defined by ASCO guidelines: Levit et al 2019).
- * Archival biopsy (ideally from the same site that C1D15 biopsy will be taken) that were taken after completion of all prior standard of care treatments will be accepted as a baseline biopsy.
5. Adequate organ and marrow function [Note: for Module 3 the samples must be collected within 10 days prior to the start of study treatment]:

- AST/ALT $\leq 3 \times$ ULN for patients with no Liver Metastasis or AST/ALT $\leq 5 \times$ ULN for patients with Liver Metastasis. [Note: for Module 3, AST/ALT must be $\leq 2.5 \times$ ULN for patients with no Liver Metastasis]
- Total Bilirubin $\leq 1.5 \times$ ULN (with the exception of patients with Gilberts disease [$\leq 3 \times$ ULN])
- Serum Creatinine $\leq 1.5 \times$ ULN
- ANC $\geq 1.5 \times 10^9/L$
- Platelets $> 100 \times 10^9/L$

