5.4 Core Exclusion Criteria

Participants are excluded from the study if any of the following criteria apply:

1. Prior therapy with a compound of the same mechanism of action as RXC004.
2. Patients at higher risk of bone fractures, including;
 - a) Patients with Vitamin D [25(OH)D₃] deficiency defined as < 30 nmol/L (< 12 ng/mL). [Note - Patients who fail on this criterion can be given supplementation and be retested within the screening window]
 - b) Patients with a corrected serum calcium level of < 2 mmol/L and serum magnesium level of < 0.60 mmol/L.
 - c) Patients with osteoporosis (as defined by a T-score of < -2.5 at any of the 3 following sites, all of which must be assessed: L/R total hip, L/R femoral neck, lumbar spine (L1-4) by DEXA scan) or history of fragility fractures (any fracture occurring with low-level trauma or as a result of falling < standing height)
 - d) Patients with ongoing or a history of clinically significant hyperparathyroidism, Pagets disease or osteomalacia. Patients with a prior diagnosis of hyperparathyroidism, Pagets disease or osteomalacia, considered by the investigator to have no increased bone fragility risk, may be included.
3. Any known uncontrolled inter-current illness or persistent clinically significant toxicity related to prior anti-cancer treatment (as assessed by the Investigator) which in the investigator's opinion makes it undesirable for the patient to participate in the study.
4. Patients who have any history of an active (requiring treatment) other malignancy (except any in-situ carcinoma, non-melanoma skin carcinoma, and early prostate cancer with a normal PSA) within 2 years of study entry.
5. Patients with known or suspected brain metastases
6. Use of anti-neoplastic agents (including immunotherapy and investigational agents) within 3 weeks prior to the first dose of study treatment, or any residual AEs from prior anti-cancer therapies that have not resolved to Grade ≤ 1 . Use of any investigational drugs within 3 weeks prior to the first dose of study treatment is also

- prohibited. Note: COVID-19 vaccinations that are authorised but not approved should not be considered as investigational agents for the purposes of study eligibility assessment.
7. Patients with a known hypersensitivity to any RXC004 excipients.
 8. Patients with a contra-indication for denosumab treatment including:
 - Known hypersensitivity to denosumab or any of the excipients
 - Severe untreated hypocalcaemia

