5.5 Module 3 Specific Exclusion Criteria

Participants are excluded from Module 3 (RXC004 + pembrolizumab) if any of the following criteria apply:

14. Patients with any contraindication to the use of pembrolizumab as per approved label (Summary of Product Characteristics or equivalent).
15. Has received prior therapy with an anti-PD-1, anti-PD-L1, or anti-PD-L2 agent or with an agent directed to another stimulatory or co-inhibitory T-cell receptor (e.g., CTLA-4, OX 40, CD137), and was discontinued from that treatment due to a Grade 3 or higher irAE.

16. Has received prior radiotherapy within 2 weeks of start of study treatment or have had a history of radiation pneumonitis. [Note: Participants must have recovered from all radiation-related toxicities and not require corticosteroids. A 1-week washout is permitted for palliative radiation (\leq 2 weeks of radiotherapy) to non-central nervous system (CNS) disease.]
17. Has a diagnosis of immunodeficiency or is receiving chronic systemic steroid therapy (in dosing exceeding 10 mg daily of prednisone equivalent) or any other form of immunosuppressive therapy within 7 days prior the first dose of pembrolizumab in this study.
18. Has severe hypersensitivity (\geq Grade 3) to pembrolizumab and/or any of its excipients.
19. Has an active autoimmune disease that has required systemic treatment in past 2 years (i.e., with use of disease modifying agents, corticosteroids or immunosuppressive drugs). Replacement therapy (e.g., thyroxine, insulin, or physiologic corticosteroid replacement therapy for adrenal or pituitary insufficiency) is not considered a form of systemic treatment and is allowed.
20. Has a history of (non-infectious) pneumonitis / interstitial lung disease that required steroids or has current pneumonitis / interstitial lung disease.
21. Has an active infection requiring systemic therapy.
22. Patients with a history of allogeneic tissue/solid organ transplant.
23. Patients with active infections, including tuberculosis, HIV, HBV, or HCV. Patients with a resolved HBV infection (defined as presence of hepatitis B core antibody [HBcAb] and absence of HBV surface antigen [HBsAg] or negative on PCR for HBV DNA) are eligible. Patients positive for HCV antibody are eligible only if PCR is negative for HCV RNA.

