### 3.2.1.3 Objective Response Rate

ORR is defined as the proportion of patients with a BOR of CR or PR. Confirmation of response is required for declaring PR or CR as the BOR. Responses on subsequent treatments after discontinuing will not be included.

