#### 4.9 Prior and Concomitant Radiotherapy and Procedure

Prior and concomitant radiotherapy will be summarized and listed for the FAS.

The following prior radiotherapy variables will be described:

- Number of patients having a history of radiotherapy
- Intent of prior radiotherapy
- Sites of prior radiotherapy

The following concomitant radiotherapy variables will be described:

- Number of patients having a concomitant radiotherapy
- Intent of concomitant radiotherapy
- Sites of concomitant radiotherapy

Concomitant procedure will be listed for the FAS.

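### No visible rule keeps radiation shrinkage of a target lesion out of best overall response, so ORR (primary in Module 3) can be biased upward

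*Protocol*

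**What the plan says.** **On study, all modules.** Protocol 5.6.3.1 states: "No other chemotherapy, or other anticancer therapy, including radiation therapy (except local treatment to a symptomatic solitary lesion". Nothing there requires the treated lesion to be a non-target lesion.

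**Entry and baseline.** Protocol 5.1, inclusion 3, asks for "At least one lesion that is measurable by RECIST 1.1 at baseline (within 6 weeks prior to start of study treatment". One target lesion is therefore enough, and the reference scan may be 6 weeks old.

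**Before first dose.** For Module 3, Protocol 5.5 excludes a patient who "Has received prior radiotherapy within 2 weeks of start of study treatment", and adds that "A 1-week washout is permitted for palliative radiation" outside the central nervous system. Modules 1 and 2 have no exclusions of their own. The core washout in Protocol 5.4 is "Use of anti-neoplastic agents (including immunotherapy and investigational agents) within 3 weeks prior to the first dose of study treatment", which does not name radiotherapy.

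**Analysis.**
- SAP 3.2.1.2 builds best overall response from the investigator's overall response at each visit and requires confirmation at least 4 weeks later.
- SAP 3.2.1.3 makes one exclusion for other treatment: "Responses on subsequent treatments after discontinuing will not be included".
- SAP 4.11.3.1 (percentage change) always uses the screening sum as reference. The SAP Appendix defines PR against the baseline sum.
- The Appendix selects target lesions by size, organ coverage and repeatability. Neither it nor Protocol Appendix D mentions irradiated lesions.
- SAP 4.9 summarises and lists radiotherapy, including "Sites of concomitant radiotherapy", but no endpoint uses these data.
- SAP 4.11.2 places primary efficacy on the full analysis set.

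**The concern.** A target lesion can be measured at screening, irradiated, and then compared with its pre-radiation size. If the sum falls by 30% and stays down for 4 weeks, the plan followed to the letter records a confirmed response to study treatment. In Module 3 that response counts in the primary endpoint of a single-arm comparison with an external rate, and there is no control arm in which the same artefact would show.

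The protocol already accepts the principle for another local procedure: inclusion 4 and the schedule footnotes keep biopsies away from RECIST target lesions. Radiotherapy has no matching safeguard. Response is investigator-assessed in an open-label trial, so a rule chosen after such cases are seen would carry less weight than one fixed in advance.

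**Working it through.** **1. The plan's own figures.** The two pembrolizumab response rates in Protocol 2.2.4.4 reproduce: 3/23 = 13.0% (exact 95% CI 2.8 to 33.6%) and 6/104 = 5.8% (2.1 to 12.1%). Protocol 12.11.1 takes about 10% as the combined benchmark, and that figure is used below. The numbers of patients, the targets and the cut-offs are redacted. The stated error rates (0.06/0.10 in Module 1, 0.06/0.20 in Module 2) therefore cannot be checked, and this point does not dispute them.

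**2. Time available between baseline scan and first dose** (maximum scan age 42 days, less the washout).
- Module 3: 42 − 14 = 28 days; palliative, 42 − 7 = 35 days.
- Modules 1 and 2: 42 − 21 = 21 days if the 3-week washout for agents is read to cover radiotherapy; up to about 42 days if it is not.

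These are maxima. On-study time comes on top in every module.

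**3. When one irradiated lesion alone gives PR.** Let the lesion make up a share w of the baseline sum, with the other target lesions unchanged. Required shrinkage = 0.30 / w. For k equal lesions, w = 1/k:

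| Target lesions (k) | Shrinkage needed |
|---|---|
| 1 | 30% |
| 2 | 60% |
| 3 | 90% |
| 4 | 120% (impossible) |
| 5 | 150% (impossible) |

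A persisting non-target lesion does not prevent this: in SAP Appendix Table 3, PR in target lesions with non-progressing non-target lesions and no new lesion is an overall PR.

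**4. Effect on ORR.** One patient adds 1/N: 1/30 = 3.3 points, 1/20 = 5 points. For an illustrative decision rule, assume a true rate of 10%, the smallest cut-off with type I error of at most 0.10, a fraction f of patients with an irradiated target lesion, and a fraction q of those otherwise non-responding becoming PR. The apparent rate is 0.10 + 0.90 × f × q. With f = 5 to 10% and q = 30 to 60%, it runs from 0.10 + 0.90 × 0.05 × 0.30 = 11.35% to 0.10 + 0.90 × 0.10 × 0.60 = 15.4%.

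| N | Go at | False-go risk, no radiotherapy effect | With effect |
|---|---|---|---|
| 20 | 5 or more | 0.043 | 0.07 to 0.18 |
| 30 | 6 or more | 0.073 | 0.12 to 0.31 |

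N, cut-off, f and q are all assumptions. The table shows sensitivity, not an expected bias.

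**5. Effect on PFS.** Progression requires a 20% rise from the nadir. Take two equal target lesions of size 1, with the first irradiated.
- First lesion unchanged: the second must reach 2 × 1.2 − 1 = 1.4, a 40% growth.
- First lesion shrinks 30% with no scan at the lower sum: 2 × 1.2 − 0.7 = 1.7, a 70% growth (later progression).
- Lower sum of 1.7 recorded first as nadir: 1.7 × 1.2 − 0.7 = 1.34, a 34% growth (earlier progression).

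The direction depends on scan timing.

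**The case against.** The other side has several good points.

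- **PFS has a stated rule.** SAP 3.2.1.1 runs PFS to progression or death whether or not another anticancer treatment intervenes. That is a treatment-policy choice, not an omission. A reader might infer that radiotherapy inflates 6-month PFS in Modules 1 and 2. The documents do not support that: the nadir can bring progression forward, and new or non-target progression counts regardless of the target sum. This objection stands.
- **Exposure is limited.** The exception covers one lesion, up to five target lesions are followed, inclusion 4 normally requires a further non-target lesion for biopsy, and response must be confirmed. All true. Confirmation helps only if the shrinkage reverses, and one to three target lesions remains a possible case.
- **The pre-dose windows are theoretical.** The schedule footnotes prefer a scan close to first dose, and in Modules 1 and 2 the opening rests on silence about radiotherapy rather than on a permission. This stands.
- **A rule may exist elsewhere.** RECIST 1.1 is cited in general, the imaging guidelines and deviation specification are not supplied, and the evaluable-set definition is redacted. It would therefore be too strong to say that no rule exists anywhere. But none is visible for the full analysis set, which carries the primary analysis.
- **Decisions use all the data, and radiotherapy is listed.** Such patients would be visible, but the reported ORR would still include them.

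**Conclusion.** The gap is real for ORR. As written, the visible rules can credit radiation shrinkage of a target lesion as a confirmed response, and the error can only raise ORR. It matters most in Module 3, where ORR is primary; in Modules 1 and 2 ORR is secondary. The size is 3.3 to 5 points per affected patient at an assumed N of 20 to 30, mainly in patients with one to three target lesions. The documents give no frequency; it is probably low, so the expected bias may be small even though one patient can matter near a cut-off. For 6-month PFS the conclusion is only that radiotherapy can alter the result, in either direction. The point warrants a pre-specified analysis rule; it does not question the permission to give radiotherapy.

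**What to change.** **Response rule (SAP 3.2.1.2, 3.2.1.3 and Appendix).** If a target lesion is irradiated after the baseline scan, before or after C0D1, later assessments of that lesion may support PD but not CR or PR. A response first documented afterwards counts only if the non-irradiated target lesions alone meet the criterion; otherwise the patient is a non-responder for ORR. This keeps responses that the untreated lesions support, needs no re-imaging and leaves eligibility alone.

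**PFS.** Keep the stated rule as primary. Add a supportive 6-month PFS analysis that handles patients with an irradiated target lesion differently, for example with the irradiation counted as an event, and report how many there are.

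**Data.** SAP 4.9 shows patient counts, intent and sites, but no date and no link to a lesion. Confirm that the eCRF records both, so that these patients can be flagged.

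**Consistency.** Protocol 7.1 stops study drug when alternative anticancer therapy starts, and its relation to the exception in 5.6.3.1 is not stated. The two must be reconciled, because the reading also decides whether the exclusion in SAP 3.2.1.3 can apply to such a patient.

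**Cost.** SAP wording, one programmed flag if the data allow it, and one supportive table. A few patients may lose responder status, making ORR slightly less favourable.

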5.6.3.2 COVID-19 Vaccinations

COVID-19 vaccination is permitted before or during study treatment, with the exception of live or live-attenuated vaccines and replication-competent vector vaccines, which are prohibited within 30 days of starting study treatment and while on study treatment.

As COVID-19 vaccines are often prioritised for cancer patients, vaccination prior to the first

dose of study treatment is advisable. Where possible, COVID-19 vaccinations should be given at least 72 hours before starting study treatment and study treatment should not commence until any acute adverse effects from vaccination have resolved to at least Grade 1. If this is not possible, investigators should follow their local prescribing information and policies when considering whether a patient on study treatment should receive a COVID-19 vaccination. If COVID-19 vaccination is given during the study (including the screening period), then please ensure that all the relevant information is recorded in the concomitant medication eCRF (i.e. vaccine name, manufacturer, date(s) given and dose).

5.6.4 Other Lifestyle Considerations

Patients taking RXC004 are advised to avoid exposure to direct sunlight and the use of tanning equipment.

5.7 Screen Failures

[figure not shown]
Screen failures are defined as participants who consent to participate in the clinical study but are not subsequently enrolled in the study. A minimal set of screen failure information is required to ensure transparent reporting of screen failure participants to meet the CONSORT publishing requirements and to respond to queries from regulatory authorities. Minimal information includes demography, screen failure details, eligibility criteria, and any SAE.

Individuals who do not meet the calcium and/or vitamin D3 laboratory criteria for participation in this study may be retested after starting calcium/vitamin D3 supplementation. Repeating laboratory tests within the screening period will not be considered as a rescreen.

5.8 Pre-Screening Genetic Testing for Module 1

For Module 1, all enrolled patients' tumours will be required to have a mutation in the RNF43 gene. Eligible patients will be identified by either a central genetics screening approach or local laboratory assessments.

Central Testing - UK

CCI [REDACTED]

Data from central genetic screening will be shared with investigators to aid future treatment decisions.

CCI [REDACTED]

CCI [REDACTED]

CCI [REDACTED]

Local Testing - UK

Patients with predicted loss of function RNF43 mutations from other local testing will also be eligible to enter the study, provided that the assay used for testing has adequate analytical validation for this purpose (i.e. fully CCI [REDACTED] for the purpose of investigating RNF43 mutations; partially CCI [REDACTED] for their analytical performance or having achieved a minimum validation specification of >90% for Analytical Sensitivity / PPA and >95% for Analytical Specificity / NPA for the detection of the aberrations in the genes of interest and performed in an ISO accredited, CLIA or CAP accredited lab). If patients have insufficient CCI [REDACTED] as is often the case for patients with pancreatic cancer, an RNF43 mutation that has been detected in CCI [REDACTED] by a commercial plasma testing panel will be accepted for enrolment, provided the test meets the validation specifications described above. If aberrations are detected by local tests that are not included in the list in Appendix F, these may be included in the study on discussion with the Sponsor, if they are predicted to lead to a loss of function in the RNF43 protein based on pre-determined criteria.

CCI [REDACTED]

CCI [REDACTED]

CCI [REDACTED]

Central Testing – Australia

Potential participants for Module 1 will be identified via their participation in the MoST Framework Protocol screening programme (Australia New Zealand Clinical Trials Registry: ACTRN12616000908437). All pre-screening activities (listed below) will be conducted as part of the MoST Framework Protocol screening programme:

- Pre-screening informed consent

- CCI [REDACTED]
- Genetic screening for RNF43 mutations

CCI [REDACTED]

CCI [REDACTED]

If patients have insufficient CCI [REDACTED] as is often the case for patients with pancreatic cancer, an RNF43 mutation that has been detected in CCI [REDACTED] may be accepted for enrolment, subject to Sponsor notification.

For Module 2 and Module 3, potential subjects may be identified via their participation in the MoST Framework Protocol screening programme, or recruited from outside of the MoST Framework Protocol screening programme.

